All subjects aged 12 years and older, with at least 365 days of data availability before index date (ID) [ID defined as the date of the latest vaccine dose administered] AND data availability from 12/2020 onwards (i.e. the time when the roll-out of the vaccination campaign started) in the respective database will be included.

	Phase II C3-002 – Study Protocol							
	Author(s): [name], [name], [name]				Version: v2.1			
	Dissemination level: Public							

All studies will be carried out comparing the following cohorts, which we defined based on varying degrees of vaccine exposure and period of predominant SARS-CoV-2 variant as shown in Table 1 below.

COVID-19 vaccination history	Cohort number							
	1	2	3	4	5	6	7	8
1 dose only					x			
Complete primary vaccination course (monovalent only)	x	x	x	x		x	x	x
3rd dose, also called 1st booster (monovalent or any of the adapted, bivalent)	x	x	x	x			x	x
4th dose, also called 2nd booster (monovalent or any of the adapted, bivalent)		x						x
4th dose, also called 2nd booster (any of the monovalent)			x					
4th dose, also called 2nd booster (any of the adapted, bivalent boosters)				x				
Study period								
Start of roll-out 4 th dose/2 nd booster onwards	x	x	x	x				
XBB variant or later dominant	x	x	x	x				
Any variant dominant					x	x	x	x

*Cohorts 3 and 4 will only be created for databases where the vaccine product is reliably recorded in addition to vaccine brand.

Outcomes 1-2 will be assessed in cohorts 1-2 (and 3-4 where available), outcomes 3-7 will be assessed in cohorts 5-8.

Unvaccinated groups will not be used as a comparator in our study for vaccine effectiveness research because they may be very different from vaccinated individuals regarding their risk of infection with SARS-Cov-2. This study therefore focusses on the association of varying degrees of vaccine exposure and COVID-19 related outcomes.

Study period:

Period of “start of roll-out 4th dose/2nd booster dose onwards”: from 01/08/2022 - last available data for each database.

Period of “XBB variant or later dominant”: 01/03/2023 - last available data for each database. Note: This period is not covered by any of the data cuts onboarded for DARWIN EU at the time of protocol submission.

Period of “any variant dominant”: 01/01/2021 (when the wider roll-out of the vaccination campaign started) - last available data for each database.

Statistical analyses:

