8.2 Study Setting and Data Sources

This study will be conducted using routinely collected data from 3 databases in 3 European countries. All databases were previously mapped to the OMOP CDM.

1. Clinical Practice Research Datalink (CPRD GOLD), United Kingdom
2. Integrated Primary Care Information Project (IPCI), The Netherlands
3. Sistema d'Informació per al Desenvolupament de la Investigació en Atenció Primària (SIDIAP), Spain

Detailed information on data sources is described in [Table 8.2.1](#).

Database selection

The selection of databases for this study was performed based on data reliability and relevance for the proposed research question among those databases onboarded and available within DARWIN EU. The selected databases fulfil the criteria required for the availability of key information on exposures (i.e. complete recording of vaccines including date and brand), outcomes (except for hospitalization), and covariates, while covering different settings and regions of Europe.

Records on SARS-CoV-2 infection and vaccination will be available in all databases. We have previously published studies showing that these databases can generate reliable evidence on COVID-19 research¹⁻⁷⁻¹⁰. Specifically, the availability of COVID-19 tests results, and linked vaccination records through national/regional immunization program (CPRD, SIDIAP) increased the reliability of the identified study exposures. Information on hospitalization will be available in SIDIAP and IPCI, which provides primary care records with (linked) hospitalization information.

No SARS-CoV-2 variant information from sequencing is available in any of the databases. We will therefore use calendar period with predominance of variants as a proxy for SARS-COV-2 variants in this study.

Information on vaccine products (i.e. monovalent/bivalent booster) are not reliably recorded in the databases, but only the vaccine brand. We will therefore use the number of vaccine doses in combination with vaccine brand for this study.

Potential for future study repetition

This study could be replicated in the future to include additional databases provided those are onboarded for DARWIN EU and fulfill the selection criteria as outlined above.

	Phase II C3-002 – Study Protocol	
	Author(s): [name], [name], [name]	Version: v2
	Dissemination level: Public	

Table 8.2.1. Description of the selected data sources.

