Country	Name of Database	Justification for Inclusion	Health Care setting	Type of Data (EHR, claims, registries)	Number of active subjects	Feasibility count of outcome/exposure (if relevant)	Data lock for the last update	Contributing to objectives
United Kingdom	CPRD GOLD	Complete records on SARS-CoV-2 infection, Covid-19 vaccination, and outcome events of interest (excl. hospitalization for COVID-19)	Primary care	EHR	3M	Covid-19: 360,198 Comirnaty: 2,822,947 Spikevax: 311,069	01/2023	1-2 for outcome “COVID-19 related death” only, 4-6
The Netherlands	IPCI	Complete records on SARS-CoV-2 infection, Covid-19 vaccination, and outcome events of interest	Primary care	EHR	1.39M	Covid-19: 941,329 Comirnaty: 1,173,104 Spikevax: 463,315	12/2022	1-6
Spain	SIDIAP	Complete records on SARS-CoV-2 infection, Covid-19 vaccination, and outcome events of interest; Include inpatient admission information.	Primary care + linkage to hospital data	EHR	5.8M	Covid-19: 3,865,976 Comirnaty: 6,548,545 Spikevax: 3,371,395	06/2022	1-6

	Phase II C3-002 – Study Protocol	
	Author(s): [name], [name], [name]	Version: v2
		Dissemination level: Public

Clinical Practice Research Datalink GOLD, United Kingdom (University of Oxford)

The Clinical Practice Research Datalink (CPRD) is a governmental, not-for-profit research service, jointly funded by the National Institute for Health and Care Research and the Medicines and Healthcare products Regulatory Agency, a part of the Department of Health, United Kingdom (UK) (<https://cprd.com>). CPRD GOLD¹¹ comprises computerized records of all clinical and referral events in primary care in addition to comprehensive demographic information and medication prescription data in a sample of UK patients (predominantly from Scotland (52% of practices) and Wales (28% of practices). The prescription records include information on the type of product, date of prescription, strength, dosage, quantity, and route of administration. Data from contributing practices are collected and processed into research databases. Quality checks on patient and practice level are applied during the initial processing. Data are available for 20 million patients, including 3.2 million currently registered patients. Approval for this study was granted via the Research Data Governance Process.

Integrated Primary Care Information Project (IPCI), The Netherlands (Erasmus)

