8.6.3. Other covariates, including confounders, effect modifiers and other variables (where relevant)

Demographics

Patients' age at index date and sex will be identified.

Geographic location

We will use geographic location, e.g. GP surgery or healthcare regions to account for local vaccination, infection and testing rates.

Predominant SARS-CoV-2 variant

Calendar time will be used as a proxy to define exposure to the predominant variant, including "Alpha and earlier variants", "Delta", "Omicron" and "XBB variant or later dominant" for databases with sufficient recent data. Time periods are specified in section 8.3 Study Period.

Health conditions pre-index date

Individuals' history of the comorbidities will be identified over three time periods prior to the index date, and will be used for summary characterisation and calculation of large-scale propensity scores:

- 1) 30 days prior to one day prior index date,
- 2) 365 days prior to one day prior index date,
- 3) all available days observed up to one day prior to index date.

A range of health conditions will be assessed using the time windows above. Among these, the following conditions will be identified for summary characterisation: anxiety, asthma, chronic obstructive pulmonary disease, chronic kidney disease, chronic liver disease, COVID-19, atrial fibrillation, cancer (excluding non-melanoma skin cancers), dementia, depressive disorder, diabetes, GERD, heart failure, hypertension, hypothyroidism, inflammatory bowel disease (crohn's disease or ulcerative colitis), myocardial infarction, venous thromboembolism, stroke, transient ischaemic attack (TIA), rheumatoid arthritis, osteoporosis, alcohol or drug substance misuse and obesity.

Medications pre-index date

Pre-existing medication use will be identified using 2 time windows, defined as 365 days to one day prior to index date, and 30 days to 1 day prior to index date, and will be used to provide summary characterisation for patients and calculation of large-scale propensity scores.

Immunocompromised status at the index date

People who are immunocompromised at the index data will be defined by the recording of certain conditions or certain conditions plus treatments prior to index date. People will be considered immunocompromised if they have *one or more* of the following conditions recorded within 365 days prior to index date:

	Phase II C3-002 – Study Protocol	
	Author(s): [name], [name], [name]	Version: v2.1

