8.8.3 Objectives 1-2: Vaccine effectiveness to prevent severe infection

Objectives 1 and 2 will assess the effectiveness of a 4th COVID-19 vaccine dose in people with 3 vaccine doses.

Study population

All people with a 3rd vaccine dose of Comirnaty or Spikevax will be included from the source population. Cohorts will be generated separately for Comirnaty and Spikevax, respectively.

Study inclusion: Sequential matching

Inclusion will be conducted using a sequential matching design, with similar designs being used in previous studies assessing vaccine effectiveness. Previous research showed matching to adequately reduce measured confounding in vaccine effectiveness research when including key variables such as geographic location²⁴.

Matching process using key confounders and Propensity Scores

For each calendar week starting from the day when a 4th vaccine dose (i.e. 2nd booster vaccine) became available/recommended in the respective country, people will be assigned to two cohorts: people who received a 4th vaccine dose during that week and people who did not receive a 4th dose.

Using the first day of the respective week as “preliminary” index date for non-boostered people, and the date of the 4th dose for booster-vaccinated people, the following inclusion criteria will be applied:

	Phase II C3-002 – Study Protocol	
	Author(s): [name], [name], [name]	Version: v2.1
		Dissemination level: Public

- At least 365 days of data availability in the respective database
- At least 90days of time elapsed since the previous vaccine dose (i.e. the 3rd or 4th vaccine dose)
- At least 90days of time elapsed since the last record of a clinical diagnosis of COVID-19 or positive SARS-COV-2 test.

Among those people in the cohorts who received or not received a 4th dose and met the inclusion criteria, non-boostered people will be matched 1:1 to a person receiving their 4th dose, based on key confounders and large-scale propensity scores using nearest neighbor matching, with caliper width 0.2 standard deviation. Key confounders will comprise but are not limited to:

- Age (e.g. 5-year age bands)
- Sex (exact)
- Geographic location (exact)
- Previous vaccine brands (e.g. homologous or heterologous vaccination scheme)
- Time from previous vaccination
- History of conditions for prioritization for vaccination
- immunocompromised status
- previous SARS-CoV-2 diagnosis (>90days before index date)

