Large-scale propensity scores (PS) will be computed to estimate the probability of receiving a 4th vaccine dose. Covariates to be included in the large-scale PS will be selected from co-medications and comorbidities recorded prior to cohort-specific index dates. Among those, covariates with a prevalence below 0.5% in the study population will be omitted. Logistic regression with LASSO regularization will then be used for variable selection. The list of selected covariates will be manually screened by 2 epidemiologists/clinical domain experts to exclude potential instrumental variables.

The same procedure will be conducted in the calendar week after, with previously non-boostered people being allowed to be included in the booster cohort once they change exposure status. Non-boostered people can only be matched once to a booster counterpart during the whole study. With matching, non-boostered counterparts will be assigned the date of when the booster counterpart received their 4th vaccine dose as their “final” index date (index date for the matched pair).

All booster and matched non-boostered people from sequential weekly matching will be combined into the booster and non-boostered cohort for subsequent analyses. The study inclusion and sequential matching process is illustrated in [Figure 8.8.3.1](#) below.

[figure not shown]

	Phase II C3-002 – Study Protocol	
	Author(s): [name], [name], [name]	Version: v2.1
	Dissemination level: Public	

Figure 8.8.3.1 Study inclusion and sequential matching process

	Phase II C3-002 – Study Protocol	
	Author(s): [name], [name], [name]	Version: v2.1
		Dissemination level: Public

Follow-up

In the matched cohorts, people will be followed up from their index date until the earliest of

- End of their observation (i.e. date of data extraction, death)
- 2nd booster vaccination for unvaccinated group, 3rd booster for vaccinated group etc.
- COVID-19 related hospitalization or death, with outcome date being defined as the date of first COVID-19 diagnosis/positive test related to hospitalization or death.

Follow-up will be censored for the matched pair if one counterpart is censored, but not if one counterpart experiences the outcome.

Outcomes

The outcomes are defined in detail in section 8.6.2.

COVID-19 related hospitalization will be assessed for SIDIAP and IPCI. COVID-19 related death will be assessed for CPRD, IPCI and SIDIAP.

Statistical Analyses

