Objective 1: Vaccine effectiveness

Cox proportions hazard models will be used to calculate hazard ratios (HR) for the outcomes of COVID-19 related hospitalisation and COVID-19 related death.

Negative control outcomes will be used as an additional measure to measure any potential residual confounding. NCO are outcomes not causally associated with the exposure of interest²⁶, here COVID-19 vaccination. However, their association with vaccination is ideally impacted by the same type of unmeasured confounding, e.g. healthcare-seeking behavior, as the vaccination-outcome association²⁷. In the scenario of potential unmeasured confounding being detected by NCO, empirical calibration²⁵ for HR might be considered to minimise bias.

Vaccine effectiveness will be calculated as $1 - HR$. Kaplan Meier plots and/or cumulative incidence plots will be used to illustrate survival analyses.

The proportional hazard assumption will be tested visual investigation of log(-log) plots. In the scenario of substantial violation of the proportional hazard assumptions, alternative models/model adaptations will be used.

Objective 2: Waning of vaccine effectiveness

Hazard ratios will be calculated for subsequent time windows after index date, i.e. in bi-weekly intervals. Monthly intervals will be used in case of small event counts to increase sample size and power if needed. Vaccine effectiveness will be calculated as $1 - HR$.

Kaplan Meier plots and/or cumulative incidence plots will be used to illustrate survival analyses.

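### The propensity score is limited to co-medications and comorbidities, and no individual measure of consulting or SARS-CoV-2 testing is named for matching, although the outcomes depend on a recorded infection

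*Protocol*

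**What the plan says.** Section 8.8.3 matches each person receiving the next dose to one person not dosed in that calendar week, using named key confounders together with a large-scale propensity score. For the score, "Covariates to be included in the large-scale PS will be selected from co-medications and comorbidities recorded prior to cohort-specific index dates". The abstract repeats this, and sections 8.8.4 and 8.8.5 take over the same process. Section 8.6.3 is consistent with it: health conditions and medications are the only variable groups assigned to the score, and of medications it says they "will be used to provide summary characterisation for patients and calculation of large-scale propensity scores". The covariate table (Table 7) lists demographics, location, variant period, comorbidity, co-medication and immunocompromised status.

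The matching list outside the score is open: "Key confounders will comprise but are not limited to" age, sex, location, previous brands, time from previous vaccination, priority conditions, immunocompromised status and earlier SARS-CoV-2 diagnosis. Location has a stated purpose: "We will use geographic location, e.g. GP surgery or healthcare regions to account for local vaccination, infection and testing rates".

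In explaining negative control outcomes under Objective 1, section 8.8.3 says "their association with vaccination is ideally impacted by the same type of unmeasured confounding, e.g. healthcare-seeking behavior". On the data themselves, section 8.2 relies on "the availability of COVID-19 tests results, and linked vaccination records through national/regional immunization program (CPRD, SIDIAP", and says that CPRD GOLD "comprises computerized records of all clinical and referral events in primary care". IPCI and SIDIAP are described as primary-care electronic health records.

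**The concern.** How often a person consults and tests can influence both whether the next dose is taken and whether an infection is recorded. The second link matters here because each outcome in section 8.6.2 and sections 8.8.3 to 8.8.5 runs through a recorded diagnosis or positive test: hospitalisation and death with COVID-19, death after a COVID-19 admission, and diabetes or cardiovascular events after SARS-CoV-2 infection.

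A person with few contacts also accumulates fewer recorded conditions and prescriptions. Balance on those two domains can therefore pair a healthy recipient with a comparator who only looks healthy on record. If testing and consulting differ between arms, effectiveness can be understated where recording dominates, or overstated where comparators are frailer or less engaged with care. Proxies for this behaviour appear to be in the data but are not named for use.

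**Working it through.** The protocol gives no bias figure, event count or sample size on this point, so there is nothing of its own to reproduce. The check has a textual part and an illustration.

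**Text**

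| Question | What the protocol shows |
|---|---|
| Which domains feed the score? | Co-medications and comorbidities (abstract, 8.6.3, 8.8.3) |
| Any individual contact or test count? | None in 8.6.3, Table 7 or the key-confounder list |
| COVID-19 test results held? | Yes (8.2); negative results not confirmed |
| Primary-care contacts held? | Explicit for CPRD GOLD; inferred for IPCI and SIDIAP from their being primary-care records |
| Non-COVID vaccinations held? | Not stated |
| Other safeguards? | Negative controls for all objectives; calibration optional in 8.8.3 to 8.8.5, though stated as planned in the abstract for Objectives 1 and 2 |
| Sensitivity analyses? | None planned (8.8.6) |
| Healthy user/adherer bias? | Checklist item 7.2 marked not applicable |

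**Illustration 1: an imbalanced care-seeking trait (all inputs assumed)**

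Let p1 and p0 be the prevalence of the trait in recipients and comparators after matching, and RR its effect on the recorded outcome. Then

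HR_obs = HR_true × B, with B = [1 + p1(RR − 1)] / [1 + p0(RR − 1)].

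Take p0 = 0.5 and p1 between 0.6 and 0.8.

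- Trait lowers the outcome, weak: p1 = 0.6, RR = 0.8 gives B = 0.88/0.90 = 0.978.
- Trait lowers the outcome, strong: p1 = 0.8, RR = 0.5 gives B = 0.60/0.75 = 0.800.
- Trait raises the recorded outcome, weak: p1 = 0.6, RR = 1.25 gives B = 1.15/1.125 = 1.022.
- Trait raises the recorded outcome, strong: p1 = 0.8, RR = 2.0 gives B = 1.80/1.50 = 1.200.

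| True VE | B = 0.800 | B = 0.978 | B = 1.022 | B = 1.200 |
|---|---|---|---|---|
| 0% | 20.0% | 2.2% | −2.2% | −20.0% |
| 20% | 36.0% | 21.8% | 18.2% | 4.0% |
| 67.8% | 74.2% | 68.5% | 67.1% | 61.4% |

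The last row uses, for scale only, the hospitalisation effectiveness from the Nordic study cited in section 6. Matching on the trait sets p1 = p0, and B becomes 1 for the part that is measured.

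**Illustration 2: under-recording in comparators (assumed)**

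If comparators' infections are recorded at a fraction q of the rate in recipients, HR_obs = HR_true / q. For a true HR of 0.70 (VE 30%), q = 0.9 gives 0.70/0.9 = 0.78 (VE 22%), and q = 0.8 gives 0.70/0.8 = 0.875 (VE 12.5%).

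**The case against.** Several points on the other side are sound. Both arms have already accepted the same number of earlier doses, which narrows differences in vaccine acceptance. Time since last dose, previous brands, earlier diagnosis and location are matched, and location may be as fine as the GP surgery. Conditions and prescriptions in the 30 and 365 days before index arise from contacts, so the score carries some information on use of care. The key-confounder list is open and could be completed in an analysis plan. Negative controls are planned throughout, and section 11 concedes residual confounding.

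These narrow the gap but do not close it. Location is there to reflect local testing rates, not individual behaviour. The candidate pool for the score is stated positively, unlike the key-confounder list. Negative controls act after matching, and one that needs no recorded infection may miss a difference in SARS-CoV-2 testing.

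A reader might go further in five ways that the documents do not support:

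- **That the records hold other vaccinations, such as influenza.** Section 8.2 describes only SARS-CoV-2 vaccination.
- **That comparators are refusers.** They are people not dosed that week. They may enter the dosed cohort later, and follow-up is censored at that dose.
- **That the study declares healthcare-seeking beyond its reach.** The sentence in 8.8.3 is a general account of how negative controls work.
- **That the protocol contradicts itself.** It sets aside unvaccinated comparators because "they may be very different from vaccinated individuals regarding their risk of infection with SARS-Cov-2". That does not claim that groups defined by successive doses are exchangeable.
- **That effectiveness is biased by a known amount in a known direction.** Section 11 regards COVID-19 hospitalisation as unlikely to be under-reported, and says that Objectives 4 to 6 will use only infections recorded before 02/2022, ahead of the fall in recorded home tests. Under-recording in comparators may therefore be smaller for these outcomes than Illustration 2 assumes.

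**Conclusion.** The point holds as a gap in the stated confounder set. The score is confined to two domains, no individual healthcare-use covariate is named, and recorded proxies are described for at least part of the data. Arms may therefore remain different in consulting and testing behaviour when every outcome depends on a recorded infection.

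The size is unknown. Bias factors of 0.80 to 0.98 or 1.02 to 1.20 follow only from the assumed prevalences and risk ratios above, and the sign depends on whether the trait mainly protects or mainly increases recording. This is a cheap improvement worth making before the code is run. It does not show that the planned estimates are invalid.

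**What to change.** In section 8.8.3, and by reference in 8.8.4 and 8.8.5, add two covariates to the propensity score, kept regardless of LASSO selection:

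1. the number of primary-care contacts in the 365 days before index;
2. the number of SARS-CoV-2 tests of any result in the same window, in databases that hold negative tests.

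Leave the week before index out of both counts, so that activity around the vaccination visit is not counted. Add prior influenza vaccination only in databases confirmed to record it. List these variables in section 8.6.3 and Table 7, and report their balance after matching with that of the other covariates.

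The cost is a few derived variables and possibly slightly fewer matched pairs. Contact counts reflect frailty as well as care-seeking, so balance on them reduces the problem without fully isolating behaviour. The negative controls remain necessary.

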Large-scale propensity scores (PS) will be computed to estimate the probability of receiving a 4th vaccine dose. Covariates to be included in the large-scale PS will be selected from co-medications and comorbidities recorded prior to cohort-specific index dates. Among those, covariates with a prevalence below 0.5% in the study population will be omitted. Logistic regression with LASSO regularization will then be used for variable selection. The list of selected covariates will be manually screened by 2 epidemiologists/clinical domain experts to exclude potential instrumental variables.

With matching, non-boostered counterparts will be assigned the date of when the boostered counterpart received their 4th vaccine dose as their “final” index date (index date for the matched pair).

In the matched cohorts, people will be followed up from their index date until the earliest of

- End of their observation (i.e. date of data extraction, death)
- next vaccine dose (4th vaccine dose for non-boostered group, 5th vaccine dose for boostered group)
- COVID-19 related hospitalization or death

	Phase II C3-002 – Study Protocol	
	Author(s): [name], [name], [name]	Version: v2.1
		Dissemination level: Public

Follow-up will be censored for the matched pair if one counterpart is censored, but not if one counterpart experiences the outcome.

The same procedure will be conducted in the calendar week after, with previously non-boostered people being allowed to be included in the booster cohort once they change exposure status. Non-boostered people can only be matched once to a booster counterpart during the whole study.

All booster and matched non-boostered people from sequential weekly matching will be combined into the exposed and unexposed cohort for subsequent analyses.

Outcomes:

- COVID-19 related hospitalization will be assessed for SIDIAP and ICPI.
- COVID-19 related death will be assessed for CPRD, IPCI and SIDIAP.

Vaccine effectiveness analyses:

Cox proportions hazard models will be used to calculate hazard ratios (HR) for the outcomes of COVID-19 related hospitalisation and COVID-19 related death.

Negative control outcomes and empirical calibration for HR will be used as an additional measure to measure and minimise any potential residual confounding.

Kaplan-Meier plots and/or cumulative incidence plots will be used to illustrate survival analyses.

Vaccine effect waning:

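### The pair rule keeps boosted partners of comparators with an outcome in follow-up, so the Objective 2 window hazard ratios can drift only towards apparent waning, by an uncertain and probably small amount

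*Protocol*

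**What the plan says.** Section 8.8.3 lets each person's follow-up run to the earliest of three events. The first is end of observation: "End of their observation (i.e. date of data extraction, death". The second is the next dose: "2nd booster vaccination for unvaccinated group, 3rd booster for vaccinated group etc". The abstract makes clear that this means the 4th dose for comparators and the 5th for boosted people: "next vaccine dose (4th vaccine dose for non-boostered group, 5th vaccine dose for boostered group". The third is the outcome: "COVID-19 related hospitalization or death, with outcome date being defined as the date of first COVID-19 diagnosis/positive test related to hospitalization or death".

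The pair rule is then added: "Follow-up will be censored for the matched pair if one counterpart is censored, but not if one counterpart experiences the outcome".

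Three other features matter. Comparators are expected to cross over, "previously non-boostered people being allowed to be included in the booster cohort once they change exposure status". Pairs are formed "based on key confounders and large-scale propensity scores using nearest neighbor matching, with caliper width 0.2 standard deviation", so the two members share much of their measured risk. Waning is read from successive windows: "Hazard ratios will be calculated for subsequent time windows after index date, i.e. in bi-weekly intervals", with monthly windows if events are few. Section 8.8.3 specifies Cox models and mentions neither stratification by pair nor censoring weights. Section 8.8.6 plans no sensitivity analyses.

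**The concern.** The exception for outcomes does not act equally in the two arms.

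- **Comparator has the outcome.** Its follow-up is over, so it can no longer be censored at a 4th dose. The boosted partner stays until their own outcome, a 5th dose or the end of data.
- **Boosted person has the outcome.** The comparator stays, but its own 4th dose still removes it.

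Boosted people left without a counterpart come from pairs selected because one member had the event, so they carry above-average risk. As intact pairs leave through 4th doses, these people form a growing share of the late boosted risk set. The comparator risk set has no matching build-up. Objective 2 draws its conclusion from the late windows, where this imbalance is largest. Negative control outcomes are planned to detect residual confounding and are not designed to detect this change in the risk sets.

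**Working it through.** The protocol states no event rate, cross-over rate or expected HR for this point, so there is no figure of its own to reproduce. The check is a model of matched pairs with no true waning.

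**Inputs from the protocol:** the censoring and pair rules, the window HRs and the unstratified Cox model of section 8.8.3; the start date of 01/08/2022 (abstract, study period); the data locks in Table 8.2.1.

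**Assumed inputs, none in the protocol:** true HR constant at 0.50; pair-shared log-normal risk with mean 1 and log-scale SD of 1.0-1.5; average comparator severe-outcome hazard of 0.02-0.05% per week (about 10-26 per 1000 person-years); comparator 4th-dose hazard c of 5-10% per week.

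**Formulas.** For a pair with comparator hazard l, at time t since index:

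- Comparators at risk: exp(-(l+c)t). This covers intact pairs and comparators whose boosted partner had the outcome.
- Boosted at risk: exp(-HR·l·t) × [exp(-(l+c)t) + l/(l+c) × (1 - exp(-(l+c)t))]. The second term in brackets is the boosted people whose comparator had the outcome before a 4th dose.
- Window HR: HR × (mean l among boosted at risk) / (mean l among comparators at risk), averaging over the distribution of l.

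**Results over the eight corners of the assumed ranges:**

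| Weeks since index | Lowest corner (0.02%, SD 1.0, 5%) | Highest of the other corners | Highest corner (0.05%, SD 1.5, 10%) |
|---|---|---|---|
| 12 | 0.502 | 0.518 | 0.529 |
| 17 | 0.503 | 0.529 | 0.557 |
| 22 | 0.505 | 0.549 | 0.602 |

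**One cell traced.** In the highest corner at week 17, boosted people without a counterpart are 2.09% of the boosted risk set and carry 7.75 times the risk of intact pairs. The boosted mean is raised by 1 + 0.0209 × (7.75 - 1) = 1.141. The comparator set is raised by 1.024, through comparators whose boosted partner had the outcome. The HR is 0.50 × 1.141 / 1.024 = 0.557.

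**Rarer outcomes.** At week 17, 5 per 1000 person-years gives 0.502-0.514, and 1 per 1000 gives at most 0.503.

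**Simulation of the highest corner**, 6 million pairs, rate ratios in successive 4-week windows:

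- Plan's rule: 0.51, 0.51, 0.51, 0.52, 0.58, 0.60.
- Both members ended at the first outcome: 0.51, 0.50, 0.49, 0.48, 0.52, 0.51.

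**Second grid.** With true HR 0.40, 144 settings were run, varying rate, uptake, spread of risk, length of follow-up and whether high-risk comparators are dosed sooner. The late HR was at or above 0.40 in every setting under the plan's rule, and 0.400 in every setting when the pair ended at the first outcome. At 0.42 years, 5 per 1000 person-years with 80% uptake gives 0.402-0.420, and 10 per 1000 with 95% uptake gives 0.410-0.572.

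**How late can anyone be observed?** Counting from 01/08/2022, week 22 falls on 02/01/2023.

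- SIDIAP (lock 06/2022): no follow-up in this period.
- IPCI (lock 12/2022): at most 152 days / 7 = 21.7 weeks.
- CPRD (lock 01/2023): at most 183 days / 7 = 26.1 weeks, and it contributes COVID-19 related death only.

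These are maxima for people indexed on the first day. Later entrants have less.

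**The case against.** The strongest reply concerns size. Every rate above is assumed, the largest figure needs the top of all three ranges at once, and the stated locks leave week 22 almost unobserved. The simulation used 6 million pairs, whereas CPRD and IPCI together hold 3 + 1.39 = 4.39 million active subjects, so real late windows would be far noisier than the drift. All of this stands.

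Keeping a person in follow-up after a partner's event is also a defensible choice that retains person-time and later events. The first-event remedy is exact only if pair members have the same risk, and matching aligns measured covariates only. With partly shared risk, the bias shrinks and the correction is approximate. That stands too.

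Three stronger readings are tempting and are not supported:

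- **That any waning found would be an artefact.** The calculations fix the direction of the drift, and its size depends on rates that the protocol does not give.
- **That every comparator death leaves the partner in follow-up.** Deaths other than COVID-19 related deaths count as end of observation, so they do end the pair.
- **That Objectives 3-6 are distorted more because infections are common.** Sections 8.8.4 and 8.8.5 carry over the inclusion process and sequential matching. The pair-censoring sentence appears only under Objectives 1-2, and Table 7.1 B and C give an individual end of follow-up. Infection (Objectives 4-6) and hospitalisation (Objective 3) are there for context, the primary outcomes are rarer composites, and no waning windows are planned.

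The protocol also does not say outright what a hospitalised survivor's later 4th dose does to the partner. That it does nothing is the natural reading, because the survivor's own follow-up has already ended.

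**Conclusion.** The point holds as a one-directional bias of uncertain size in the Objective 2 window HRs. With pair-shared risk and comparator cross-over, the rule as written pushes those HRs upward, and none of the settings tried reversed it. Under the main assumptions, a constant effectiveness of 50% would read about 47-50% at week 12 and 44-50% at week 17. It would reach about 40% only at week 22 in the most extreme corner. With rarer outcomes the shift is negligible. The overall HR of Objective 1 moves from 0.50 to about 0.52 at most. The correction is worth making because Objective 2 rests on these windows, the drift imitates the finding being sought, and no planned analysis would reveal it.

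**What to change.** For the Objective 2 window HRs, fit the Cox model stratified by matched pair, or equivalently end both members' follow-up at the first outcome in the pair. Make this the main analysis, or at least a pre-specified sensitivity analysis.

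Do not apply first-event ending to the Kaplan-Meier or cumulative incidence plots. Censoring a person at a correlated partner's event is informative and would understate incidence in both arms.

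Add two clarifications: what a comparator's 4th dose after its own outcome does to the partner's follow-up, and whether the pair-censoring rule applies to Objectives 3-6. If it does, use the same pair-stratified model for their HRs.

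The cost is a sentence or two of text, a small change to the model code, and the person-time and events that follow a partner's outcome. That person-time is under 1% for severe outcomes under the assumptions above.
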